10.14.4. Discontinuation of Study Intervention and Participant Discontinuation from the Substudy

If the investigator or the participant/caregiver judges that CCI training is unsuccessful or the self-administration dosings cannot be performed independently, the participant will no longer participate in the CCI self-administration substudy

10.14.5. Secondary Efficacy Assessments**10.14.5.1. PROs****All Participants from AMAG and AMAM**

The CCI will be collected for each set of CCI injections performed by a participant/caregiver for both training and independent administrations.

CCI

10.14.6. Complaint Handling

See Section 8.3.8.

10.14.7. Analyses

Analyses presented for this substudy will be descriptive, including frequency counts and percentages, and use the modified intent-to-treat population in participants who have enrolled in the **CCI** substudy.

CCI

In participants who have completed **CCI** training, analyses of successful administration with an **CCI** may be presented by administration attempt.

10.15. Appendix 15: Country-specific Requirements

This appendix is applicable for sites in EU-member states and Turkey.

Note: Deletions to the main protocol sections are identified by ~~strikethrough format~~ and additions by underlined text.

10.15.1. Hungary, Latvia, and Romania

This section describes protocol changes applicable for participants in study sites in Hungary, Latvia, and Romania

This table describes the changes and provides a rationale for the changes

Protocol Section Number and Name	Description of the Change	Brief Rationale
5.1 Inclusion Criteria	Updated inclusion criterion [6]	To align with contraceptive use for all sites in Hungary, Latvia, and Romania

The revised text in the following sections show the changes applicable for participants at study sites in Hungary, Latvia, and Romania.

5.1 Inclusion Criteria

[6] Contraception: Contraceptive use by men or women should be consistent with local regulations regarding the methods of contraception for those participating in clinical studies.

a. Male Participants:

~~No male contraception is required except in compliance with specific local government study requirements. Agree to use a reliable method of birth control during the study and for at least 16 weeks following the last dose of the study drug.~~

b. Female Participants:

Women of childbearing potential (WOCBP, defined as all adult females unless they are WNOCBP as defined below) may participate if they meet the following criteria:

A. must test negative for pregnancy prior to initiation of treatment as indicated by a negative urine pregnancy test at Visit 1/Week 0 of this study

AND

~~B. must agree to either remain abstinent, if complete abstinence is their preferred and usual lifestyle, or remain in same-sex relationships, if part of their preferred and usual lifestyle, without sexual relationships with males. Periodic abstinence (for example, calendar, ovulation, symptothermal, or postovulation methods), declaration of abstinence just for the duration of a trial, and withdrawal are not acceptable methods of contraception;~~

OR

~~must use a combination of 2 effective methods of contraception or 1 highly effective method of contraception for the entirety of the study, where at least 1 method must be highly effective and the other method is effective or highly effective. Abstinence or eContraception must continue for 16 weeks following completion of study drug administration for 16 weeks.~~

- i. Effective methods of contraception may include barrier methods such as male or female condoms with spermicide, diaphragms with spermicide, or cervical sponges (which usually are made with spermicide). The barrier method must include use of a spermicide to be counted as one effective method.
- ii. Highly effective (<1% failure rate) methods of contraception (at least one of which must be used) include
 - female sterilization
 - combination oral contraceptive pill
 - progestin-only contraceptive pill (mini-pill)
 - implanted contraceptives
 - injectable contraceptives
 - contraceptive patch (only women <198 pounds or 90 kg)
 - vasectomy (if only sexual partner)
 - fallopian tube implants (if confirmed by hysterosalpingogram)
 - combined contraceptive vaginal ring, or
 - intrauterine devices
- iii. Ineffective forms of contraception, whether used alone or in any combination, include
 - spermicide alone
 - periodic abstinence
 - fertility awareness (calendar method, temperature method, cervical mucus, or symptothermal)
 - withdrawal
 - postcoital douche or
 - lactational amenorrhea

Women **not of childbearing potential** (WNOCBP) may participate and include those who are:

A. infertile due to surgical sterilization (total hysterectomy, bilateral salpingo-oophorectomy, bilateral salpingectomy, bilateral oophorectomy, or tubal ligation)^a, have a congenital anomaly such as Müllerian agenesis

OR

B. postmenopausal^b – defined as either:

- i. a woman at least 40 years of age with an intact uterus, not on hormone therapy, who has had either:
 - cessation of menses for at least 1 year, without an alternative medical cause
 - at least 6 months of spontaneous amenorrhea with a follicle-stimulating hormone level >40 mIU/mL
- ii. a woman 55 years or older not on hormone therapy, who has had at least 6 months of spontaneous amenorrhea, or

- iii. a woman at least 55 years of age with a diagnosis of menopause prior to starting hormone replacement therapy.

^a Note that if it has been less than 6 weeks post-surgical bilateral oophorectomy with or without hysterectomy, she will be required to use contraception until she has reached 6 weeks since the procedure.

^b For the purpose of defining the length of time of amenorrhea to determine postmenopausal status, only count time in which the woman was not taking medications such as oral contraceptives, hormones, gonadotropin-releasing hormone, anti-estrogens, SERMs, or chemotherapy that could induce transient amenorrhea.

10.15.2. Netherlands and Turkey

This section describes protocol changes applicable for adult participants in study sites in Netherlands and Turkey

This table describes the changes and provides a rationale for the changes

Protocol Section Number and Name	Description of the Change	Brief Rationale
7.2. Participant Discontinuation/Withdrawal from the Study	Added information about inadvertently enrolled participants	To remove inadvertently enrolled participants from the study

The revised text in the following sections show the changes applicable for adult participants at study sites in Netherlands and Turkey.

7.2 Participant Discontinuation/Withdrawal from the Study

If the sponsor or investigator identifies a participant who did not meet enrollment criteria and was inadvertently enrolled into AMAX, the participant must be withdrawn from the study in order to comply with local regulations.

10.15.3. Czech Republic

This section describes protocol changes applicable for adult participants in study sites in the Czech Republic.

This table describes the changes and provides a rationale for the changes

Protocol Section Number and Name	Description of the Change	Brief Rationale
1.3 Schedule of Activities	Updated tuberculosis risk assessment and yearly screening for active and latent TB in participants	Updated in accordance with regulatory requirements in the Czech Republic
5.1 Inclusion Criteria	Updated inclusion criteria [6] b	Revised in accordance with regulatory requirements in the Czech Republic
8.2.4 Chest Radiography	Added Czech Republic-specific details for chest radiography	Updated in accordance with regulatory requirements in the Czech Republic
8.2.6 Tuberculosis Testing	Added Czech Republic-specific details for tuberculosis testing and removed general instructions for initial screening test	Updated in accordance with regulatory requirements in the Czech Republic

The revised text in the following sections show the changes applicable for adult participants at study sites in the Czech Republic.

1.3 Schedule of Activities (SoA)

1.3.1 Visit 1 through Visit 9 CCI

Table AMAX.1.1. Schedule of Activities - Visit 1 through Visit 9 CCI

Procedures	Schedule of Activities ^a													
	Visit Number		V1 ^b		V2	V3	V4		V5	V6	V7	V8	V9	
Visit Type	Office – Screening/ V1 ^a	Office - Dosing/V1 ^b	Office	Office	Phone	Office	Phone	Office						
Week Relative to Study Drug Start ^c	CCI													
Day with Visit Tolerance Interval (VTI)														
All Participants (X); AMAM Rollover Participants Only (M); AMAG Rollover Participants Only (G); Optional (Opt) (See footnotes for additional key details)														
TB Risk Assessment Monitoring ⁱ	X ^{af}	X ^{ah}	X				X	X	X	X	X	X		
Yearly screening for active and latent TB in participants in the Czech Republic*	X											X		

Abbreviations: AEs = adverse events; CT = computed tomography; CXR = chest x-ray; CCI [REDACTED]; IGRA = interferon gamma release assay; NA = Not applicable; PK = pharmacokinetic; TB = tuberculosis; TST = tuberculin skin test; V = Visit

* Participants from the Czech Republic will be screened for active and latent TB infection annually, including at Visits 1 and 9. This will include the assessment of medical history, AEs, and clinical risk, physical examination, and a TB test as described Tuberculosis Testing section (Section 8.2.6 of main protocol and Section 8.2.6 of this appendix). Participants who had a TST must return 48 to 72 hours after placement to have their test results read by a pulmonologist. A chest X-ray may be performed if clinically indicated. A CT scan may be performed as an alternative based on regional standard of practice

a Please see detailed instructions provided by the sponsor for calculation of visit dates. Also, note that unscheduled assessments can be performed during scheduled visits, see Table AMAX.1-3 for details.

b V1 is a split visit, occurring on at least 2 office visits on different dates. Screening procedures are to be performed at the first part of V1, called Screening/V1a, in order to have results available to confirm eligibility prior to dosing. For AMAM-originating participants, it is recommended that V1a screening procedures be on the same date as AMAM V17. V1 dosing is performed at the Dosing/V1b visit. For both AMAM and AMAG-originating participants, the timing for AMAX V1a and V1b must allow for first AMAX dosing (V1b) within no more than CCI [REDACTED] from the last dosing in the originating study. It is required that all screening assessments, including laboratory test results are reviewed to confirm eligibility from both the final visit of the originating study as well as AMAX V1a, as applicable, prior to dosing at V1b. For participants originating from AMAM, CCI [REDACTED] [REDACTED]. Note that some assessments may be required at both V1a and V1b. Refer to footnotes for details. To accommodate potential lab delays and/or needs for retesting, please plan for at least 10 business days to obtain lab results after initial samples are received at the laboratory, and up to 5 business days for endoscopy results after receipt of video.

c All activities should be completed prior to any study drug administration unless otherwise stated.

d See footnote b for definitions of the V1 Screening visit (V1a) and the V1 Dosing visit (V1b). V1 dosing (V1b) is defined as Day 1. All V1 screening activities need to be performed prior to dosing, including all assessment retesting (if needed), with results available prior to dosing such that the total interval from last dose in the originating study to first dose in AMAX is no more than CCI [REDACTED]. Please see detailed instructions provided by the sponsor for calculation of subsequent visit dates.

i At V1 and throughout the study, participants will be assessed for risk factors for TB (Section 10.5, Appendix 5). If the participant has a risk factor(s) or any TB-related signs or symptoms identified as part of the discussions of preexisting conditions or AEs, or as part of the standard physical exam, the investigator should conduct a thorough exam to evaluate for TB, including examination of peripheral lymph nodes and documentation of body temperature. If there are relevant physical findings or other factors that the investigator feels requires testing and imaging, an IGRA or TST and a CXR should be performed (Table AMAX.1-3 Unscheduled assessments). A CT scan can be performed as an alternative to the CXR, based on regional standard of practice (Section 8.2.6).

af Collect/assess at AMAX V1a if not performed at the last visit of the originator study.

ah If more than 14 weeks will have elapsed between last collection/assessment and the first AMAX dosing, additional procedures must be performed again prior to the V1b dosing. See sponsor guidance regarding sample collection kits or data entry for items that need to be collected again at V1b. Investigator medical judgment should be used regarding whether the repeat lab results should be available and reviewed prior to dosing (review prior to dosing not needed for PK, immunogenicity, CCI [REDACTED], or fecal calprotectin).

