5.1.5 Missing Data Imputation

Intercurrent events (FDA 2017) are events which occur after the study intervention initiation and make it impossible to measure a variable or influence how it should be interpreted. Section 1.1 includes intercurrent events for the primary and secondary endpoints. The missing data methods described below may be used to address the intercurrent event strategies proposed for this study.

Non-Responder Imputation

A hybrid estimand strategy will be used to handle binary endpoints:

- Patients who discontinue study treatment due to reasons other than commercial availability and extraordinary circumstances including study treatment supply issues and the site termination, are categorized as treatment failures after discontinuation. As such, these patients are not considered missing from the perspective of the estimand of interest.
- The hypothetical strategy will be used to handle the ICE of study treatment discontinuation due to commercial availability and extraordinary circumstances including study treatment supply issues and the site termination. Participants with the ICE will be excluded from analysis for timepoints of interest after the ICE. The assumption behind this approach is that measurements after this ICE are missing completely at random and thus the estimation can be implemented using observed values.

^a Unless otherwise specified, these treatment arms are not included in the modeling to estimate treatment effect for MMRM and ANCOVA analysis. Also these treatment arms may be excluded from some tables or figures to simplify the output.

A small number of patients who completed study treatment up to the time point of interest but are sporadically missing the binary endpoint data will still require imputation. These patients will be imputed using NRI.

Modified Baseline Observation Carried Forward (mBOCF)

As a primary analysis for continuous variables, the ANCOVA with mBOCF approach will be used for handling missing data. For continuous endpoints a hybrid estimand strategy is used:

- For ICEs of study intervention discontinuation due to reasons other than commercial
 availability and extraordinary circumstances including study treatment supply issues and
 the site termination, the composite strategy will be used such that measurements after the
 ICEs will return to baseline. As such, these patients are not considered missing from the
 perspective of the estimand of interest.

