Measure	Description	Variable CDAI total score	CDAI total score is based on the CDAI questionnaire in Appendix 7 in Section 6.7. It also utilizes the standard weights table in that section. 1.Patient-reported items from diary - the most recent 7 days are included (possibly nonconsecutive) out of the 4 weeks prior to corresponding visit after removing the day(s) of the endoscopy prep, the day of endoscopy procedure, and the 2 days following the endoscopy procedure. See Appendix 9. 2. Physician-reported questionnaire – from up to 4 weeks prior to actual visit 3.Hematocrit - central (or secondarily local) lab Hematocrit value associated with the Visit; if neither available, use closest result from 4 weeks prior to visit up to 12 weeks after visit except for Week 12; For Week 12/V4, 4 weeks before or after this visit. 4. Weight –weight associated with the Visit;	Definition of missing CDAI total score will be missing if any of its components are missing. If none of the options in Section 4 of the CDAI questionnaire is checked, it will be assumed that no extra- intestinal manifestations were present.
			4. Weight –weight associated with the Visit; If not available, closest to the visit in 6 months before or after the visit except for Week 12; For Week 12 use 12 weeks before or after this visit	
		Change from baseline in CDAI total score	Change from baseline in CDAI score is defined as CDAI score – baseline CDAI score.	Missing if CDAI total score is missing at baseline or at time point.

Measure	Description	Variable	Derivation / Comment	Definition of missing
		Clinical response by	Clinical response by CDAI is defined as a	Missing if CDAI total
		CDAI	decrease from baseline in the CDAI total	score is missing at
			score ≥ 100 and/or a CDAI total score ≤ 150 .	baseline or at time
				point.
		Clinical remission	Clinical remission by CDAI is defined as	Missing if CDAI total
		by CDAI		score is missing at time
				point.
		AP average	Description of AP average is provided as	Missing if less than
			part of the definition for clinical remission	4 days of data are
			by PRO.	available at time point
		Change from	Change from baseline in AP average is	Missing if AP average
		baseline in AP	defined as AP average – baseline AP	is missing at baseline
		average	average.	or at time point
		SF average	Description of SF average is provided as	Missing if less than 4
			part of the definition for clinical remission	days of data are
			by PRO.	available at time point

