6.9 Appendix 9: Study Visit or Week Definition for Daily Diary

CDAI-SF, CDAI-AP, CDAI Well-Being, CCl and additional measures are collected using Patient Daily Diary, entries will be mapped to study week by the following:

Visit Number /	Diary Data	Start Day	End Day
Week Number	Collection		
Baseline ¹		NA	NA
Visit 1 ¹ / Week 0		NA	NA
Visit 2 / Week 4	Electronic Diary	Max (Date of First Dosing, Week 4	Week 4 Assessment
		Assessment Date – 28 days	Date – 1 day
Visit 3 / Week 8	Electronic Diary	Max (Week 4 Assessment Date, Week	Week 8 Assessment
		8 Assessment Date – 28 days	Date – 1 day
Visit 4 / Week 12	Electronic Diary	Max (Week 8 Assessment Date, Week	Week 12 Assessment
		12 Assessment Date – 28 days	Date – 1 day
Visit 5 / Week 20 ²	1-Day paper diary	NA	NA
Visit 6 / Week 28 ²	1-Day paper diary	NA	NA
Visit 7 / Week 36 ²	1-Day paper diary	NA	NA
Visit 8 / Week 44 ²	1-Day paper diary	NA	NA
Visit 9 / Week 52	14-Day paper	Max (Week 44 Assessment Date, Week	Week 52 Assessment
	diary	52 Assessment Date – 28 days	Date – 1 day
Visit 10 / Week 60 ²	1-Day paper diary	NA	NA
Visit 11 / Week 68 ²	1-Day paper diary	NA	NA
Visit 12 / Week 76	14-Day paper	Max (Week 68 Assessment Date, Week	Week 76 Assessment
	diary	76 Assessment Date – 28 days	Date – 1 day
Visit 13 / Week 88 ²	1-Day paper diary	NA	NA
Visit 14 / Week 100	14-Day paper	Max (Week 88 Assessment Date, Week	Week 100 Assessment
	diary	100 Assessment Date – 28 days	Date – 1 day
Visit 15 / Week 112 ²	1-Day paper diary	NA	NA
Visit 16 / Week 124	14-Day paper	Max (Week 112 Assessment Date,	Week 124 Assessment
	diary	Week 124 Assessment Date – 28 days	Date – 1 day
Visit 17 / Week 136 ²	1-Day paper diary	NA	NA
Visit 18 / Week 148 ²	1-Day paper diary	NA	NA
Visit 19 / Week 156	14-Day paper	Max (Week 148 Assessment Date,	Week 156 Assessment
	diary	Week 156 Assessment Date – 28 days	Date – 1 day

¹ Baseline will be the Baseline from AMAM or AMAG. For Visit 1 the summarized value for each relevant variable will be the last available value for the patient from study AMAG or AMAM.

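### If the visit weight is missing, the SAP's CDAI fallback window can hold no scheduled weight at Week 12, or at Week 156 without continued access, so NRI counts the participant as a non-remitter

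*Protocol*

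**What the plan says.** SAP Section 6.1 (Appendix 1), CDAI total score, item 4, uses the weight associated with the visit. If there is none, it takes the weight "closest to the visit in 6 months before or after the visit except for Week 12". The exception reads "For Week 12 use 12 weeks before or after this visit". The same entry says "CDAI total score will be missing if any of its components are missing".

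SAP Section 5.1.5 covers participants still on treatment whose binary endpoint is sporadically missing: "These patients will be imputed using NRI". The sensitivity method mNRI uses multiple imputation for them, and the as-observed analysis leaves them out at that visit.

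The weight rows of the Protocol's Schedule of Activities (Sections 1.3.1 and 1.3.2) give V1a, V4, V9, V12, V14, V16 and V19. The extracted Year 1 table is broken; V4 and V9 are read from its alignment with the clinician CDAI row. That row has an entry at V1b, and the weight row has none. The footnote on the entry weight says "Collect/assess at AMAX V1a if not performed at the last visit of the originator study". Footnote b of Section 1.3.1 says "V1 is a split visit, occurring on at least 2 office visits on different dates", and sites are told to plan at least 10 business days for laboratory results. Dosing at V1b is Day 1.

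SAP Section 6.9 (Appendix 9) supplies the weeks: V4 is Week 12, V9 Week 52, V12 Week 76, V14 Week 100, then "Visit 16 / Week 124", and V19 is Week 156.

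**The concern.** The fallback exists so that one missing item does not cost the whole score. It can do that only if the window contains a weight that the schedule collects. At two visits it may not. Twelve weeks back from Week 12 reaches the dosing day, but the entry weight is taken before that day. Six months back from Week 156 falls short of V16.

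A participant with complete diary, clinician items and hematocrit would then lose the CDAI for want of a weight, although an earlier one is on file. Under non-responder imputation (NRI), the main analysis, that participant counts as not in CDAI remission and not a CDAI responder. For CDAI remission in participants with, and in those without, remission at originator Week 52, the table in SAP Section 6.2 lists NRI only. There, no alternative analysis sits beside the result.

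**Working it through.** The plan states no figure to reproduce; this is date arithmetic.

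**Inputs.** Visit weeks come from SAP Section 6.9 and weight visits from the Protocol schedule. The usual visit tolerance is ±7 days, or −7 to +20 days in exceptional circumstances (Protocol Table AMAX.10-1). Twelve weeks is 84 days. Six months is 181 to 184 days, taken as about 183. Ten business days is about 14 calendar days.

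**Week 12.** Let L be the days from V1a to V1b and s the shift of V4 from its nominal date. The gap from the entry weight to V4 is 84 + L + s, against a limit of 84.
- L = 1, s = 0: 85 days, outside.
- L = 14, s = 0: 98 days, outside.
- L = 14, s = −7: 91 days, outside.
- L = 7, s = −7: 84 days, just inside.

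The entry weight is inside only if V4 is early by at least L days. With the planned lead it is outside throughout the ±7-day tolerance. The next scheduled weight is V9: (52 − 12) × 7 = 280 days later, outside.

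If the window were programmed on nominal weeks, with Visit 1 as Week 0, the gap would be exactly 84 days and the entry weight would count.

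**Week 156.** V16 is (156 − 124) × 7 = 224 days earlier. With V16 7 days late and V19 7 days early it is 224 − 14 = 210. With the exceptional-circumstances windows it is 224 − 27 = 197. All exceed 6 months. Follow-up visits V801 and V802 take no weight.

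In continued access (Protocol Section 10.13.3), weight is scheduled at V501 and V502, and is repeated at V501 if that is not the same day as V19. The timing of V502 is redacted. If it came 4 to 12 weeks after a same-day V19/V501, its weight would be 28 to 84 days later; even 24 weeks gives 168 days. All are inside.

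**Other visits.** For Week 52, V4 is 280 days back (outside) and V12 is 168 days ahead (inside; 154 to 182 with ±7 days at each visit). Weeks 76, 100 and 124 each have a scheduled weight 168 days away, inside.

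**What an old weight costs.** In SAP Section 6.7 (Appendix 7), weight enters as percentage deviation from standard weight, times 1. Take an error of 3 kg as an illustration: 3/75 × 100 = 4.0 points and 3/55 × 100 = 5.5 points.

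**What dropping the CDAI costs under NRI.** Let m be the share of participants missing weight alone and p their true remission rate. The reported rate falls by m × p. With m assumed at 1–5% and p at 30–70%, the range runs from 0.01 × 0.30 = 0.3 to 0.05 × 0.70 = 3.5 percentage points.

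**The case against.** A reader might infer more than the documents support.

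- **That the Week 156 window is empty for everyone.** It is not. The window also runs forward, and the SAP does not exclude continued-access weights. Protocol Section 10.13.1 says efficacy data are not collected in that period, so whether those weights count is unsettled. The gap is firm only for participants who do not enter continued access.
- **That Week 12 always fails.** The SAP does not say whether actual dates or nominal weeks govern, and on nominal weeks the entry weight is just inside. The 10 business days are planning advice; the firm rule is only that V1a and V1b fall on different dates. A short lead with an early V4 also puts the weight inside.
- **That the co-primary Week 52 CDAI has the same gap.** It does not, because V12 is within 6 months. The V12 weight may not yet exist at a Week 52 interim, but that is a matter of timing.
- **That every analysis scores these participants as failures.** Only NRI does.

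Weights at the AMAG 3-year office visit, and optional unscheduled weights, can also fill a window. The cost arises only when weight alone is missing. Weight and the clinician CDAI share the post-entry visits, so a missed visit will often lose both. The study tests no hypotheses, so no formal conclusion turns on this.

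All of that limits the scope and size. It does not remove the gap.

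**Conclusion.** The point holds in limited form. If the visit weight is missing, the fallback holds no scheduled weight (a) at Week 12, when actual dates are used and V1a precedes dosing by the planned lead, and (b) at Week 156 for participants who do not enter continued access. NRI then counts the participant as a non-remitter and non-responder by CDAI although a usable earlier weight exists. mNRI and the as-observed analysis are not affected in that way.

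The rate of isolated missing weight is not in the documents. The range of 0.3 to 3.5 percentage points therefore rests on assumed inputs and is not an estimate; its top needs both upper assumptions at once. The effect is probably small, and under NRI it can only lower the rate. The case for acting is that the loss is avoidable at almost no cost.

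**What to change.** In SAP Section 6.1 (Appendix 1), CDAI total score, item 4:

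- Keep the closest weight within 6 months either side of the visit, for all visits.
- Delete the separate 12-week clause for Week 12. The V1a or last originator-visit weight then falls in the window (about 98 days against about 183), while V9 at 280 days stays outside.
- Add: *if no weight falls in the window, use the most recent earlier weight.*
- State that windows use actual dates, and whether V501 and V502 weights count for Week 156.

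A simpler rule that always takes the most recent earlier weight should be avoided. At Week 52 it would replace the V12 weight, 24 weeks away, with the V4 weight, 40 weeks old.

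The cost is a few lines of SAP text and a small change to the derivation code. The downside is that in rare cases the weight used is about 14 to 32 weeks old, or 40 weeks at a Week 52 interim before V12. That is an error of a few CDAI points.
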